### 13.1.1.12 Vital Signs

Nominal Visit	Target Day	Window Definition (Study Day)
Baseline	1	Last evaluation prior to or on Study Day 1
Month 1 a	31	Study Day 2 to 106
Month 6	183	Study Day 107 to 274
Month 12	366	Study Day 275 to End of Double-blind Period Date
Month 18	548	End of Double-blind Period Date +1 to Study Day 639
Month 24	731	Study Day 640 to End of Open-label M24 Study Period Date
Month 30	913	End of Open-label M24 Study Period Date +1 to Study Day 1004
Month 36	1096	Study Day 1005 to 1187
Month 42	1278	Study Day 1188 to 1369
Month 48	1461	Study Day 1370 to 1552
Month 54	1643	Study Day 1553 to 1734
Month 60	1826	Study Day 1735 to 1917

a Any laboratory or antibody assessment done on Study Day 1 but after the administration of the investigational product will be classified into Month 1.

Data are collected every 6 months after Month 36 until the end of the primary analysis period.

### 13.2 Genant Semiquantitative Scoring Method

Both incident and prevalent vertebral fractures present on a radiograph are defined by using the Genant Semiquantitative Scoring Method ([Genant et al, 1993](#)) for each vertebra (T4 through L4) as described in the table below.

Grade	Fracture Severity	Definition
0	Normal	Normal; (Approximately less than 20% reduction in anterior, middle, and/or posterior height)
1	Mild	Approximately 20% to 25% reduction in anterior, middle, and/or posterior height
2	Moderate	Approximately 25% to 40% reduction in anterior, middle, and/or posterior height
3	Severe	Approximately 40% or greater reduction in anterior, middle, and/or posterior height

### 13.3 Reliability, Validity, and Scoring Algorithm for PRO Measurements

#### 13.3.1 OPAQ-SV

##### Reliability and Validity

The OPAQ-SV is a comprehensive instrument designed to evaluate the impact of vertebral and nonvertebral fractures on different aspects of health-related quality of life. The OPAQ-SV contains 34 questions that can be summarized into 7 scales (walking/bending, daily activities, transfer, fear of falls, back pain, body image, and independence) and 3 dimensions (physical function, emotional status, and back pain). The OPAQ-SV has been validated in osteoporotic subjects and used extensively. Internal consistency for the OPAQ-SV is high (Cronbach's alpha = 0.86; [Silverman SL, 2000](#)).

##### Question Mapping

Dimension	Scale	Questions
Physical function	Walking/bending	1 – 7
	Daily activities	8 – 15
	Transfer	16 – 19
Emotional status	Fear of falls	20 – 24
	Body image	29 – 31
	Independence	32 – 34
Back pain	Back pain	25 – 28

### Scoring Algorithm

1. Standardize the response for each question to a 0 – 100 scale according to the table below.
2. Average the standardized values within each of the 7 scales and 3 dimensions to create the summary or scale scores based on the question mapping. The score will only be calculated if  $\geq 50\%$  of the items within the scale or dimension are nonmissing. Otherwise, set the score to missing.

Question Number	Question Response	Question Score	Standardized Value
2, 5, 6, 7, 16 - 19, 25, 27, 28	All days	1	0
	Most days	2	25
	Some days	3	50
	Few days	4	75
	No days	5	100
1, 3, 4, 8, 9, 10	All days	1	100
	Most days	2	75
	Some days	3	50
	Few days	4	25
	No days	5	0
11,12, 20,21, 22, 23, 24, 29, 30, 31, 33, 34	Always	1	0
	Very often	2	25
	Sometimes	3	50
	Almost never	4	75
	Never	5	100
13, 14, 15, 32	Always	1	100
	Very often	2	75
	Sometimes	3	50
	Almost never	4	25
	Never	5	0
26	Severe	1	0
	Moderate	2	25
	Mild	3	50
	Very mild	4	75
	None	5	100

#### 13.3.2 EQ-5D-5L

##### Visual Analog Scale

Questionnaire asks respondents to rate their present health status on a vertical 0 to 100 visual analog scale of 20 cm, with 0 labeled as “Worst imaginable health state” and 100 labeled as “Best imaginable health state.” The scale is marked in increments of “1,” with values labeled at each decile. The person scoring this question must observe

the point at which the subject's hand-drawn line intersects the scale and enter the closest integer.

### 13.3.3 LAD Questionnaire

Limited activity days questionnaire evaluate subjects' back pain experience during the past 30 days and this questionnaire has been used in several clinical trials including the Fracture Intervention Trial (Nevitt MC, 2000). The responses of each question will be analyzed separately. The responses of each question are as follows:

[figure not shown]
Questions	Responses
1, 2a, 2b	If question 1 = 'Yes', then answer question 2a and 2b.  2a = Specify number of days cutting down on things due to health reasons or mark 'Don't know'  2b = Specify number of days cutting down on things due to a fracture  If question 1 = 'No' or 'Subject does not know', then answer question 3a.
3a, 3b	If question 3a = 'Yes', then specify number of nights spent in a hospital due to health reasons and then answer question 3b.  3b = Specify number of nights spent in a hospital due to a fracture.  If question 3a = 'No' or 'Subject does not know', then answer question 4a.
4a, 4b	If question 4a = 'Yes', then specify number of days staying in bed for more than half the day (NOT in a hospital) more than half of the day due to health reasons and then answer question 4b.  4b = Specify number of days spent in bed for more than half the day due to a fracture.  If question 4a = 'No' or 'Subject does not know', then questionnaire is complete.

The responses of each question will be analyzed individually.

[figure not shown]
### 13.4 Code Fragments

CCI

CCI

CCI

CCI

CCI

CCI

CCI

CCI

CCI

CCI

### 13.5 Definitions of Adjusted p-values

Hochberg procedure will be applied to adjust the p-values for the two primary endpoints, new vertebral fracture through M24 and clinical fracture through PA. For illustration purpose, the p-value for new vertebral fracture through M24 is assumed to be the smaller of the 2 p-values. The adjusted p-values will be compared to 0.05 to determine whether the endpoint is significant except the nonvertebral fracture through PA will be compared to the  $\alpha$  that is determined by the alpha spending function.

Test ID	Endpoint	Nominal p-value	Adjusted p-value
Two primary endpoints			
1	New vertebral fracture through M24	$p_1$	$\text{Min}(p_1 * 2, p_2)$
2	Clinical Fracture through PA	$p_2$	$p_2$
Secondary endpoints specified in the testing sequence			
3	Lumbar spine at Month 24	$p_3$	$\text{Max}(p_2, p_3)$
4	Total Hip at Month 24	$p_4$	$\text{Max}(p_2, p_3, p_4)$
5	Femoral neck at Month 24	$p_5$	$\text{Max}(p_2, p_3, p_4, p_5)$
6	Lumbar spine at Month 12	$p_6$	$\text{Max}(p_2, p_3, p_4, p_5, p_6)$
7	Total Hip at Month 12	$p_7$	$\text{Max}(p_2, p_3, p_4, p_5, p_6, p_7)$
8	Femoral neck at Month 12	$p_8$	$\text{Max}(p_2, p_3, p_4, p_5, p_6, p_7, p_8)$
9	Nonvertebral fracture through PA (1-sided) & information fraction = $I$	$p_9$	$\text{Max}(p_2, p_3, p_4, p_5, p_6, p_7, p_8, a * 2)$ , where $(a * \ln(1+(e-1) * I)) = p_9$

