### Power

The power for the clinical fracture and new vertebral fracture endpoint after accounting for the multiplicity adjustment are 94% and 95%. There is 91% power that both primary endpoints will be significant at the 5% level (2-sided) after accounting for multiplicity. Based on the simulation, the median time of the primary analysis is after the last enrolled subject completes the Month 24 visit. The median number of subjects having clinical fractures in the simulation at the time of the primary analysis is 396. Note that the number of clinical fractures at the time of the primary analysis will exceed 330 when 330 subjects with confirmed clinical fractures occur before the Month 24 analysis.

If both primary endpoints are significant under the Hochberg procedure, **each of the following secondary DXA BMD endpoints will be tested hierarchically at 0.05 according to the following sequence: percent change from baseline in BMD at lumbar spine at Month 24, percent change from baseline in BMD at total hip at Month 24, percent change from baseline in BMD at femoral neck at Month 24, percent change from baseline in BMD at lumbar spine at Month 12, percent change from baseline in BMD at total hip at Month 12, and percent change from baseline in BMD at femoral neck at Month 12. The power for each DXA BMD endpoints is > 99% using the 2-sample t-test.**

**If all preceding endpoints are significant**, the nonvertebral fracture endpoint will be tested using a group sequential approach at the primary analysis and the final analysis based on a 1-sided test ( $\alpha = 0.025$ ). The Lan-DeMets alpha spending function ([Lan and DeMets, 1983](#)) that approximates a Pocock boundary ([Pocock, 1977](#)), ( $0.025 * \text{LN}(1 + (\text{EXP}(1) - 1) * \text{information fraction})$ ), will be used to determine the significance level at the time of the primary analysis. Based on the number of subjects with nonvertebral fractures at the time of the primary analysis out of the total 440 planned, which represents the information fraction in the alpha spending function, the significance level will be calculated at the time of primary analysis. For example, if the information fraction is 80% at time of the primary analysis, the significance level is

0.0216. Based on the simulation, the power for nonvertebral fracture and both primary endpoints **and DXA BMD endpoints at Month 12 and Month 24** being significant is **approximately 78%** at the primary analysis.

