## Power

The power for the clinical fracture and new vertebral fracture endpoint after accounting for the multiplicity adjustment are 94% and 95%. There is 91% power that both primary endpoints will be significant at the 5% level (2-sided) after accounting for multiplicity. Based on the simulation, the median time of the primary analysis in the simulation is after the last enrolled subject completes the Month 24 visit. The median number of subjects having clinical fractures in the simulation at the time of the primary analysis is 396. Note that the number of clinical fractures at the time of the primary analysis will exceed 330 when 330 subjects with confirmed clinical fractures occur before the Month 24 analysis.

If both of the primary endpoints are significant under the Hochberg procedure, each of the following secondary DXA BMD endpoints will be tested hierarchically at 0.05 according to the following sequence: percent change from baseline in BMD at lumbar spine at Month 24, percent change from baseline in BMD at total hip at Month 24, percent change from baseline in BMD at femoral neck at Month 24, percent change from baseline in BMD at lumbar spine at Month 12, percent change from baseline in BMD at total hip at Month 12, and percent change from baseline in BMD at femoral neck at Month 12. The power for each DXA BMD endpoints is > 99% using the 2-sample *t*-test.

If all preceding endpoints are significant, the nonvertebral fracture endpoint will be tested using a group sequential approach at the primary analysis and the final analysis based on a 1-sided test ( $\alpha = 0.025$ ). The Lan-DeMets alpha spending function (Lan and DeMets, 1983) that approximates a Pocock boundary (Pocock, 1977),  $(0.025 * \text{LN}(1 + (\text{EXP}(1) - 1) * \text{information fraction}))$ , will be used to determine the significance level at the time of the primary analysis. Based on the number of subjects with nonvertebral fractures at the time of the primary analysis out of the total 440 planned, which represents the information fraction in the alpha spending function, the significance level will be calculated at the time of primary analysis. For example, if the information fraction is 80% at time of the primary analysis, the significance level is 0.0216. Based on the simulation, the power for nonvertebral fracture, both primary endpoints, and DXA BMD endpoints at Month 12 and Month 24 all being significant is approximately 78% at the primary analysis.

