If the significance of nonvertebral fracture is not demonstrated at the time of the primary analysis, the nonvertebral fracture endpoint will be tested again using a 1-sided test at the time of the final analysis. Based on the alpha level spent at the primary analysis, the significance level at final will be determined. For example, if the information fraction is 80% at the primary analysis (ie, the significance level is 0.0216 at primary), the significance level at the final analysis will be 0.0119 using software EAST 5.4 or R gsDesign package. Based on the simulation, the power for nonvertebral fracture being significant at the primary or final analysis, and both primary endpoints and DXA BMD endpoints at Month 12 and Month 24 being significant at primary analysis is approximately 84%.

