## **10. Statistical Methods of Analysis**

### **10.1 General Principles**

The analytical approach for this study will be to use inferential testing to evaluate the following:

- the effect of romosozumab treatment for 12 months followed by ALN treatment on fracture outcome as compared with ALN alone
- the effect of romosozumab treatment for 12 months on fracture outcomes as compared with ALN alone

All efficacy analyses will be performed by randomized treatment, regardless of actual treatment received.

At primary analysis, to maintain the overall significance level of 0.05, Hochberg's method will be used to evaluate the primary endpoints:

- Subject incidence of clinical fracture at primary analysis
- Subject incidence of new vertebral fracture through Month 24

If both the primary endpoints are significant at the 0.05 level (2-sided), each of the following secondary DXA BMD endpoints will be tested hierarchically at 0.05 (2-sided) according to the following sequence: percent change from baseline in BMD at lumbar spine at Month 24, percent change from baseline in BMD at total hip at Month 24, percent change from baseline in BMD at femoral neck at Month 24, percent change from baseline in BMD at lumbar spine at Month 12, percent change from baseline in BMD at total hip at Month 12, and percent change from baseline in BMD at femoral neck at Month 12.

If all preceding endpoints are significant, the nonvertebral fracture at the primary analysis will be evaluated based on a 1-sided test at the significance level determined by the alpha spending function specified in [Section 3.2.3](#). The adjusted 2-sided p-value will be provided to demonstrate the overall significance level of 0.05. All remaining secondary and exploratory efficacy endpoints will be explored at significance level of

0.05 (2-sided). If superiority of the nonvertebral fracture endpoint is achieved at the primary analysis and the study is stopped after the primary analysis has been performed, all data, including the additional safety and nonvertebral fracture data, collected after the primary analysis will be summarized descriptively. Study completion constitutes either completion of primary analysis if superiority is proven for nonvertebral fractures or until 440 subjects experience a nonvertebral fracture.

For analyses where the age stratification factor needs to be incorporated, the following general principles will be followed:

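### SAP 13.5 sends the nonvertebral adjusted p-value to the spending-function alpha, although that function is already divided out and the value belongs against 0.05

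*SAP*

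**What the plan says.** The planned rule appears in several places and is consistent. Under SAP 3.2.3 (Power), once both primary endpoints and the six BMD endpoints have passed, the "nonvertebral fracture endpoint will be tested using a group sequential approach at the primary analysis and the final analysis based on a 1-sided test", with total 1-sided alpha 0.025. The level at the primary analysis is 0.025 × ln(1+(e-1)I), where I is the number of subjects with nonvertebral fracture divided by 440. The worked example is that "if the information fraction is 80% at time of the primary analysis, the significance level is 0.0216", after which "the significance level at the final analysis will be 0.0119 using software EAST 5.4 or R gsDesign package". Protocol 10.2 takes the same count out of 440, "which represents the information fraction in the alpha spending function, the significance level will be calculated at the time of primary analysis".

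SAP 10.1 turns this into a decision rule: nonvertebral fracture "will be evaluated based on a 1-sided test at the significance level determined by the alpha spending function". Protocol 10.5.1 says the same. SAP 10.1 then gives the adjusted value a separate role: "The adjusted 2-sided p-value will be provided to demonstrate the overall significance level of 0.05".

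SAP 13.5 defines the adjusted values. For test 9 the entry is Max(p2, ..., p8, 2a), where a solves a × ln(1+(e-1)I) = p9 and p9 is the nominal 1-sided p-value. The sentence above the table reads "The adjusted p-values will be compared to 0.05 to determine whether the endpoint is significant except the nonvertebral fracture through PA will be compared" and then names the alpha from the spending function as the comparator for this endpoint.

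**The concern.** An adjusted p-value is built so that one common level, here 0.05, decides every test. The entry for test 9 follows that logic: it divides p9 by the spending fraction and doubles it to the 2-sided scale. The sentence above the table then sets this endpoint aside and refers it to the spending alpha. A programmer who follows that sentence applies the spending function once in the adjustment and again in the comparator. If alpha is the 1-sided figure, a 2-sided-scale value is also being held to a 1-sided level.

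There is a second effect. The adjusted value is a maximum, so it can never be smaller than p2 to p8. If the comparator is below 0.05, an earlier endpoint that passed at 0.05 with a p-value above that comparator blocks nonvertebral fracture whatever p9 is. Nothing else in the plan asks for this.

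Nonvertebral fracture is the last test in the confirmatory sequence. Under SAP 3.1 and 10.1, superiority on it at the primary analysis constitutes study completion; otherwise follow-up runs to 440 subjects with an event. Two readings of the SAP can therefore give opposite answers on both the claim and the continuation of the trial.

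**Working it through.** **Inputs.** 1-sided alpha 0.025, the spending function, 440 planned events and the 80% example come from SAP 3.2.3. The 27% reduction (hazard ratio 0.73) comes from SAP 3.2.2. The test 9 formula comes from SAP 13.5.

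**The plan's own figures.** L = ln(1+(e-1) × 0.8) = 0.8648, and 0.025 × 0.8648 = 0.02162, matching 0.0216. For the final level, solve P(Z1 > z1 or Z2 > z2) = 0.025 for a bivariate normal with correlation √0.8, where z1 cuts off 0.02162. The result is 0.0119, which also matches.

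**Which comparator reproduces the rule.** With a = p9/L:

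- 2a ≤ 0.05 is the same as p9 ≤ 0.025 × L, the planned boundary.
- 2a ≤ 0.025 × L (1-sided alpha) is the same as p9 ≤ 0.0125 × L².
- 2a ≤ 0.05 × L (alpha doubled) is the same as p9 ≤ 0.025 × L².

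Only 0.05 returns the planned rule at the primary analysis; for I below 1 the other two are stricter.

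**Cut-offs on p9.**

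| I | Intended (against 0.05) | Against 1-sided alpha | Against doubled alpha |
|---|---|---|---|
| 0.70 | 0.0197 | 0.0078 | 0.0156 |
| 0.80 | 0.0216 | 0.0094 | 0.0187 |
| 0.90 | 0.0234 | 0.0109 | 0.0218 |

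**A reversal.** At I = 0.80 and p9 = 0.015, 2a = 2 × 0.015/0.8648 = 0.0347. Since 0.015 is below 0.0216, SAP 10.1 declares superiority. Since 0.0347 exceeds 0.0216, the 1-sided reading of 13.5 does not.

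**Observed hazard ratio needed.** With 352 events (0.80 × 440) and equal allocation, the threshold is exp(-2z/√352). For z = 2.021, 2.081 and 2.351 it is 0.806 (intended), 0.801 (doubled) and 0.778 (1-sided).

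**Marginal power at hazard ratio 0.73.** Φ(-ln(0.73) × √352/2 - z) = Φ(2.952 - z), giving 82.4% (intended), 80.8% (doubled) and 72.6% (1-sided).

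**Joint power at the primary analysis (illustrative).** This was simulated with 4,000 subjects, 34-month accrual, dropout of 10% then 8% a year, new vertebral rates of 2.2% and 1.1% a year, one third of new vertebral fractures clinical, and BMD tests taken as passed (stated power above 99% each). The documents do not give the accrual pattern, so it is assumed. The stated values are a median of 396 clinical fractures and joint power of about 78%.

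| Nonvertebral rate per year and accrual | Median clinical fractures | Intended | 1-sided alpha | Doubled alpha |
|---|---|---|---|---|
| ALN 3.6%, HR 0.73, uniform | 397 | 76.8% | 63.1% | 73.8% |
| ALN 4.0%, HR 0.73, uniform | 432 | 80.3% | 69.7% | 78.7% |
| 4.125% and 3.025%, back-loaded | 401 | 80.0% | 68.2% | 77.8% |
| 4.125% and 3.025%, uniform | 451 | 83.0% | 71.5% | 82.0% |

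The 3.6% rate was chosen to bring the event count close to 396. The first two rows rest on 2,000 trials each and the last two on 3,000 each. In the first two rows, comparing the adjusted value with 0.05 gave the same decision as the SAP 10.1 rule in every simulated trial.

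**The case against.** The strongest reply is that the exception was meant for the nominal p-value. Its clause speaks of nonvertebral fracture being compared, not explicitly of its adjusted p-value. The table has a nominal column, and row 9 is labelled 1-sided, which suits a 1-sided spending level. Read that way, 13.5 agrees with SAP 10.1 and 3.2.3 and with Protocol 10.2 and 10.5.1, and the power loss is zero. This may well be what the authors intended. But the sentence opens with the adjusted p-values, the section exists to define them, and the nominal column is never mentioned. The text as written points to the wrong quantity.

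It is also fair that SAP 10.1 already fixes the decision rule, so harm arises only if someone programs from 13.5 instead. The relevant code is redacted, so whether that happened cannot be seen.

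The large power loss needs the least favourable reading, with a 2-sided-scale value against a 1-sided alpha. On matching scales the loss is small. The joint-power figures depend on assumed accrual and event rates, and the uniform run with 451 clinical fractures does not reproduce the plan's 396. They show the order of magnitude only.

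Finally, the error is conservative, a missed result is retested at the final analysis, and blocking by a BMD endpoint is remote given the stated power above 99%. In practice only the larger of the two primary p-values could block. All of this stands and limits the severity; none of it makes the sentence correct.

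**Conclusion.** The concern holds. As written, the comparator in SAP 13.5 for the nonvertebral adjusted p-value is wrong and disagrees with SAP 10.1 and 3.2.3. This follows from the algebra of the test 9 formula and needs no outside assumption.

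At I = 0.80, results with p9 between 0.0094 and 0.0216 (1-sided alpha) or between 0.0187 and 0.0216 (doubled alpha) receive opposite verdicts. At a hazard ratio of 0.73 and exactly 352 events, the marginal power loss is 9.8 points (82.4 to 72.6) or 1.6 points (82.4 to 80.8). The simulated joint loss is 10.6 to 13.7 points or 1.0 to 3.0 points, depending on assumed accrual and rates.

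Type I error is not inflated; the worst outcome is a missed claim at the primary analysis. The stated final level of 0.0119 presupposes 0.0216 spent at the first look, so it would not match a stricter first-look rule. This should be fixed, but it does not threaten the validity of the design.

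**What to change.** Either of two edits to SAP 13.5 is enough:

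- Delete the exception, so that the nonvertebral adjusted p-value is compared with 0.05 like every other entry in the table.
- Keep a separate rule, but state that the nominal 1-sided p9 is compared with 0.025 × ln(1+(e-1)I) once all preceding endpoints are significant at 0.05, and that the adjusted value is for display only.

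The first is simpler and matches the role SAP 10.1 gives the adjusted value. The cost is one sentence in the SAP before unblinding, and a check that the program agrees with it. Design, alpha and sample size do not change.
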